### ***Statistical Analysis Plan***

***Key Question #1:*** Does exercise training favorably alter coronary anatomy and function as determined by non-invasive imaging techniques?

***Statistical Analysis, Key Question #1.*** Myocardial blood flow using PET at rest and following dipyridamole infusion will be expressed as ml flow/100 g/min. The primary outcome, myocardial perfusion reserve, will be calculated as the ratio of the myocardial blood flow during stress (e.g. after dipyridamole) and the myocardial blood flow at rest. Differences within and between groups will be assessed using repeated measures ANOVA, with group (exercise vs. PCI) and test (baseline vs. 1-year) as factors. Post-hoc procedures will be performed using the Bonferonni method.

***Key Question #2:*** Can a program of exercise therapy improve outcomes (exercise capacity, symptoms, repeat hospitalizations, and quality of life) in patients with CAD that are equivalent or superior to PCI?

Statistical Analysis, Key Question #2. These secondary outcomes will include changes in peak  $VO_2$  and other cardiopulmonary exercise test responses (including  $VO_2$  at the ventilatory threshold, exercise time, and heart rate recovery), quality of life measures, and lipid panels. Paired tests will be used (paired t-test or Wilcoxon signed rank test) to compare continuous variables between groups at baseline. Differences between groups after the 1-year study period will be assessed by repeated measures ANOVA, with group (exercise vs. PCI) and test (baseline vs. 1-year) as factors. Post-hoc procedures will be performed using the Bonferroni method.

**Key Question #3:** Will exercise training reduce costs as compared to standard PCI after 1-year?

Statistical Analysis, Key Question #3. Comparison of costs will be made for the individual level change scores using the intervention net-costs (intervention delivery minus healthcare expense cost-savings). Cost effectiveness of the intervention will be defined by the primary outcome at the patient level. That is, changes from baseline in individual global myocardial perfusion reserve using PET at 1-year will be used to calculate the effect. Differences in costs between groups will be assessed using ANOVA.

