## RESEARCH DESIGN and METHODS

## Study Population

*Stable patients between the ages of 50 and 70 years who have lesions appropriate for PCI based on American Heart Association/American College of Cardiology criteria will be considered for the study. Only patients with a good prognosis (annual mortality <1% based on VA multivariate scores (56, 57) will be considered. Patients with left main disease or proximal LAD disease will be excluded. Additional exclusion criteria include those with unstable angina, a history of heart failure (EF ≤30%), pacemakers, atrial fibrillation, myocardial infarction within the last 3 months, diabetes, and those with orthopedic problems interfering with the ability to exercise regularly.*

**Recruitment.** *A study flow chart including screening, baseline evaluations, and procedures is presented in Appendix I. Subjects will be recruited from the following populations: 1) patients referred for a clinically-indicated stress myocardial perfusion study (nuclear, echo, or CT); and 2) patients who have a positive exercise test with >1.0 mm ST-segment deviation from baseline on a standard treadmill exercise test, estimated to have a >80% probability of disease based on VA scores (56,57). There are approximately 2,500 patients who undergo these evaluations for CAD at our facility annually, providing a large pool of potential subjects for the study. Potential subjects will be referred for PET/CTA, and baseline PET/CTA findings will confirm patients meet inclusion and exclusion criteria. If the PET/CTA studies show significant ischemia in a moderate to large territory supplied by a significantly diseased vessel, these patients will be recruited for the study.*

*PET is considered the gold standard for stress perfusion imaging. Thus, only patients who have moderate to large areas of moderate to severe perfusion defects will be recruited. In addition, only subjects who have a perfusion defect on PET supplied by a significantly diseased artery on CTA will be recruited. Only subjects actually referred for PCI will be considered for the study. A partial waiver of authorization (per HIPAA) will be obtained in order to access medical records or contact individuals for the purpose of study recruitment. A total of 64 subjects will be recruited; randomization will be stratified by age, exercise capacity, and BMI so that these variables will be matched evenly between exercise intervention and PCI groups.*

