**Cardiopulmonary Exercise Testing.** Peak  $VO_2$  will be determined at baseline and after 6 months and 1 year on a treadmill using an individualized ramp protocol with collection of continuous ventilatory gas exchange responses. A thorough clinical history, medications and risk factors will be recorded prospectively at the time of baseline exercise testing using computerized forms that include standard definitions of clinical conditions and exercise responses. In accordance with standard practice at the Palo Alto VAHCS, prior to exercise testing, patients complete a questionnaire to estimate exercise capacity; the questionnaire is used to individualize the exercise protocol which allows most patients to reach maximal effort within the recommended range of 8 to 12 minutes (58). We previously observed that this protocol provides the closest relation between measured and estimated metabolic equivalents (METs) (59). Patients will be discouraged from using the handrails for support. Medications will not be changed or stopped prior to testing. A 12-lead electrocardiogram, heart rate, and blood pressure responses will be monitored throughout the exercise test and recovery period. Ventilatory gas exchange measurements will be obtained continuously at rest, throughout exercise, and during 5 minutes of recovery. All subjects will be encouraged to give a maximal effort, and the Borg 6-20 scale will be used to quantify subjective effort (60). Standardized clinical indications for stopping will be used. ST-segment depression will be measured visually at the J junction, and slope will be determined over the following 60 ms and classified as upsloping, horizontal, or downsloping. Ventricular tachycardia will be defined as three or more consecutive premature ventricular contractions, and *frequent* premature ventricular contractions will be defined as 10% or more of the total ventricular contractions. Blood pressure will be measured manually, and exercise capacity will be measured directly using ventilatory gas exchange techniques. The exercise tests will be performed, analyzed, and reported according to a standardized protocol and utilizing a computerized database (61).

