### **Sample Size Estimates**

*Sample size estimates are based on our primary endpoint, change in global myocardial blood flow reserve from baseline using pharmacologic stress with dipyridamole, and applying variance in myocardial blood flow reserve measured by PET published previously in subjects with coronary artery disease (71,77,78). We anticipate that the overall change in the primary endpoint will be approximately 15%; this is based on previous measurements of coronary blood flow reserve using PET comparing sedentary and fit subjects cross-sectionally (77), after exercise training (78), and risk reduction interventions such as smoking cessation (96). We also anticipate that these changes will parallel the well-documented changes in exercise capacity with training in subjects with CAD (i.e. mean change in peak  $VO_2 \approx 15\%$ ) (18,19,24). Given a standard deviation of myocardial flow reserve in similar populations of 0.20 ml/g/min both at baseline and after treatment with a pre-post correlation of 0.65 (calculated from the data in reference 96), the standard deviation of the change in myocardial blood flow is 0.167. We want to detect a 15% change (absolute change of  $0.15 \times 0.9$  or 0.135) so the standardized effect size (absolute value of difference in group values for mean change divided by the standard deviation) is about 0.81. Using a 2-sided significance level of 0.05 and 80% power, 25 subjects in each group will be needed to complete the protocol.*

We anticipate that there will be a 20% dropout rate, which is typical of that in the cardiac rehabilitation literature and in accordance with our previous experience. Thus, our target enrollment will be 32 subjects in each group. The dropout rate may be lower given that compliance tends to be better in research studies compared to clinical practice, and that the subjects will receive continuous monitoring, follow-up, and encouragement to remain physically active. *Dropouts will not be included in the statistical analyses (97).*

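### The primary repeated-measures ANOVA names no primary term and ignores baseline perfusion reserve and the stratification factors; the Key Question #2 baseline comparison applies paired tests to independent arms

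*Combined protocol and SAP*

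**What the plan says.** Under Key Question #1, the Statistical Analysis Plan defines the outcome, "The primary outcome, myocardial perfusion reserve, will be calculated as the ratio of the myocardial blood flow during stress" to flow at rest, and gives the method: "Differences within and between groups will be assessed using repeated measures ANOVA, with group (exercise vs. PCI) and test (baseline vs. 1-year) as factors". Bonferroni post-hoc procedures follow. No interaction, primary contrast or covariate is mentioned.

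The Sample Size Estimates section is more specific. It describes the endpoint as "change in global myocardial blood flow reserve from baseline using pharmacologic stress with dipyridamole", and its standardized effect is the "absolute value of difference in group values for mean change divided by the standard deviation".

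Under Recruitment, in the Study Population section, "randomization will be stratified by age, exercise capacity, and BMI so that these variables will be matched evenly" between the arms. None of these three variables appears in any analysis model.

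Under Key Question #2, the plan adds: "Paired tests will be used (paired t-test or Wilcoxon signed rank test) to compare continuous variables between groups at baseline".

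**The concern.** A two-by-two repeated-measures ANOVA yields three tests: group, test (time) and their interaction. Only the interaction compares the change under exercise with the change under PCI. The plan speaks of differences both within and between groups. Key Question #1 and the principal objective ask whether exercise training improves coronary function, which reads as a within-arm question, while the Statement of the Problem and the Purpose section state a comparison with PCI. If the term is not fixed in advance, the primary p-value could be taken from an effect that has little power or that does not address the comparison.

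Baseline reserve and the three stratification factors are known before randomisation, and the plan itself assumes a pre-post correlation of 0.65. In a trial of about 50 completers sized at the edge of 80% power, leaving them out gives away precision.

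A paired test needs pairs. Stratified randomisation balances groups; it does not match individual patients. Where the arms differ in size the test cannot be computed, and where they are equal the result depends on an arbitrary ordering.

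**Working it through.** **Inputs (Sample Size Estimates).** SD 0.20 at each time point; pre-post correlation r = 0.65; difference 0.15 × 0.9 = 0.135; two-sided 5%; 80% power; 25 completers per arm; 20% dropout; 32 enrolled per arm.

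**1. The plan's own figure.**
- SD of change = 0.20 × √(2 × (1 − 0.65)) = 0.1673.
- Standardized effect = 0.135 / 0.1673 = 0.807.
- Normal approximation: n = 2 × (1.960 + 0.842)² / 0.807² = 24.1, so 25 per arm. 25 / 0.8 = 31.25, so 32 enrolled. Both figures reproduce.
- With the noncentral t distribution (48 df), power at 25 per arm is 79.8%, and 26 per arm are needed for 80%.

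**2. What each ANOVA term tests at 25 per arm.**
- *Interaction.* With two time points this is the two-sample t-test on change, so it is the test in step 1: power 79.8%. Simulated type I error is 5.0% to 5.1%.
- *Group main effect.* This averages baseline and 1 year, so the effect is (0 + 0.135) / 2 = 0.0675. SD of the patient mean = 0.20 × √((1 + 0.65) / 2) = 0.1817; standardized effect 0.372; power 25.1%; 115 per arm needed for 80%.
- *Test (time) main effect.* If both arms improve equally by 0.135, it is significant in more than 99.9% of 40,000 simulated trials, so it says nothing about exercise versus PCI.

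**3. Adjusting for baseline reserve.**
- Residual SD = 0.20 × √(1 − 0.65²) = 0.1520.
- Variance relative to change scores = (1 − r²) / (2(1 − r)) = (1 + r) / 2 = 0.825, a 17.5% reduction.
- Noncentral t with 47 df, averaged over chance baseline imbalance: power 86.1% at 25 per arm, 79.1% at 21, 81.1% at 22. So 22 per arm suffice. (Ignoring chance imbalance gives 86.8% and 21 per arm.)
- Adding three covariates that explain nothing, treated as unbalanced so that this is an upper bound on their cost: 83.6% at 25 per arm, and 24 per arm for 80%.

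Sensitivity to r, 25 per arm, baseline as the only covariate:

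| r | Variance reduction | Power, change score | Power, ANCOVA |
|---|---|---|---|
| 0.4 | 30% | 56.9% | about 71% |
| 0.65 | 17.5% | 79.8% | 86.1% |
| 0.8 | 10% | 95.9% | 97.1% |

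**4. Leaving out the stratification factors.** The documents do not say how strongly these factors predict the outcome, so this step is an assumption. If perfectly balanced factors explained 0, 10, 20 or 30% of the variance of change, the simulated type I error of the unadjusted test would be 5.0, 3.9, 2.8 or 1.9%. The test becomes conservative, not biased. With no balance on the factor, the error stays at about 5% even at 30% explained.

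**5. Paired tests on independent arms.** With arbitrary pairing of equal-sized arms, the simulated type I error remains 4.9%, so the test is not anti-conservative on average. The p-value is arbitrary, however: in one simulated data set of 32 per arm, reordering one arm moved it between 0.00004 and 0.016, against 0.002 for the two-sample t-test.

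**The case against.** The strongest reply is that the primary term is already settled. The sample-size section powers the difference in mean change, the cost-effectiveness section also defines effect as change from baseline, and post-hoc comparisons in a two-by-two design make sense only after an interaction. On that reading the 25% power describes a test nobody intends. This stands in part: the intended contrast can be inferred, and the sample size is not in error. It remains an inference, because the analysis section does not state it.

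Second, ANCOVA is an improvement on a valid test. If dropout were lower and 28, 30 or 32 per arm completed, the planned test would have 84%, 87% or 89% power. That is true, but step 3's calculation then gives 90%, 92% and 93% for ANCOVA on baseline, so the gain persists, though it shrinks. It also depends on r = 0.65, taken from a cited study, and on an SD stated in ml/g/min for an outcome that is a ratio. The variance ratio (1 + r)/2 does not depend on the unit; the power figures do depend on the SD.

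Third, the conservatism from omitted stratification factors requires both prognostic strength and close balance. Neither is assured with three factors, 64 patients, no stated cut-points and dropouts excluded. This stands: 1.9% is an extreme.

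Fourth, the paired test is a minor error because no treatment effect is estimated from it. That also stands.

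**Conclusion.** The concern holds in all three parts and should be corrected before the data are analysed.

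- **Primary term:** a gap in specification. The interaction is valid and matches the sample size, with 79.8% power at 25 per arm. The group main effect would have 25%, and the time effect does not compare the treatments. Validity here refers to the interaction among the patients analysed; the exclusion of dropouts is a separate matter.
- **Adjustment:** a loss of precision, not a bias. Under the plan's SD, correlation and difference, adjusting for baseline adds about 6 percentage points of power, or saves 4 completers per arm (22 against 26). Even if the stratification factors predict nothing, the fully adjusted model keeps 83.6%. Over r from 0.4 to 0.8 the gain from baseline adjustment runs from about 14 points to about 1.
- **Paired baseline tests:** wrong as written, but confined to the baseline comparison.

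The benefit of the stratification factors themselves cannot be computed from the documents.

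**What to change.** **Key Question #1.** State that the primary result is the adjusted group difference in 1-year perfusion reserve with its 95% confidence interval, from ANCOVA on group, baseline perfusion reserve, age, exercise capacity and BMI. If repeated-measures ANOVA is kept, state that the group-by-test interaction is the primary test and that the main effects and within-group changes are descriptive.

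**Key Question #2.** Use the same ANCOVA for continuous outcomes that have a baseline value: exercise-test responses, quality-of-life and angina scores, and lipids. The plan notes that "exercise capacity will be measured directly using ventilatory gas exchange techniques", so for peak VO2 let its own baseline value stand for exercise capacity rather than entering both. A mixed model is optional where Table 1 gives 6-month data. Repeat hospitalizations are not a continuous outcome with a baseline value and need a method of their own.

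**Baseline comparison.** Replace the paired tests with summaries by arm or, if tests are wanted, with two-sample t or rank-sum tests.

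**Cost.** SAP wording only. The baseline PET and exercise test both precede randomisation, and age and BMI must be known in order to stratify, so no new data or patients are needed.

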Given the high volume of PCI, its high cost, its lack of effect on survival and the potential for alternative treatments including exercise and risk reduction in PCI candidates, the current proposal is termed “**PCI Alternative Using Sustained Exercise**” (PAUSE). **The primary aim of PAUSE is to employ non-invasive methods to determine whether patients randomized to exercise intervention have greater improvement in coronary function and anatomy compared to those randomized to PCI.** Both groups will receive optimal medical management. We will also compare health care costs, symptoms, quality of life, and clinical outcomes between the two groups. At baseline and one year after randomization, patients will undergo an assessment of physical activity patterns and fitness using standardized questionnaires and maximal cardiopulmonary exercise testing (CPX). Patients will also undergo evaluation of coronary function and anatomy with positron emission tomography combined with computed tomographic angiography (PET/CTA). PET will be used to measure myocardial perfusion. CTA will be used to evaluate anatomical progression of atherosclerotic disease based on a qualitative scoring system of coronary artery calcium. The combination of PET/CTA provides information that previously could only be obtained invasively using coronary flow wires and invasive x-ray angiography. This will permit a non-invasive way to evaluate both functional and anatomical adaptations to exercise. Our overall objective is to demonstrate the utility of a non-invasive technology to document the efficacy of exercise therapy as an alternative treatment strategy to PCI for coronary lesions.

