Cost analyses have suggested that the current rate of increase in PCI with DES is unsustainable for the U.S. healthcare system (5). Given the high costs associated with PCI, there have been recent efforts to compare outcomes and effectiveness of PCI against non-invasive therapy. In the Occluded Artery Trial (OAT) (21), cumulative 2-year costs were \$7,000 lower in patients randomized to medical therapy versus PCI, and medical therapy was associated with slightly better quality-adjusted survival. In the primary COURAGE trial (6), PCI did not reduce the risk of mortality, myocardial infarction, or other cardiovascular events when compared to optimal medical therapy over 4.6 years of follow-up. Interestingly, in an additional sub-analysis of COURAGE assessing myocardial perfusion data (22), a greater improvement in percent of ischemic myocardium, a predictor of mortality, was observed in patients who underwent PCI. Although the myocardial perfusion results were conflicting to the main trial results, not all patients had myocardial perfusion evaluations performed and the sample in the sub-study was not randomized. In addition, the study did not include an evaluation of endothelial dysfunction, which has been associated with cardiac events and has been reported in post-PCI patients with DES. The COURAGE trial has stimulated a great deal of media attention and numerous commentaries. Interpretations of the COURAGE results range from confirmation of PCI as it is presently indicated by recognized guidelines, to recommending a greater emphasis on aggressive medical and lifestyle therapy in selected patients in lieu of PCI, to predicting a marked decline in PCIs (7,9,23).

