***VA Utilization Extractions and Cost-Savings Estimates.*** Using the VA system (CPRS), we will track the actual patient care utilization (e.g., inpatient and outpatient visits, events, hospitalizations, procedures and prescriptions) during the study period for each patient in the trial. This will permit the comparison of the expected differences in hospitalizations, physician visits, medications and ER visits. The difference in units of service (physician / primary care visits; ER visits and hospitalizations) will be valued using the Medicare national average, without differentials for teaching affiliation and geographic location, and by national average DSS values from the VA. Medical events are chronologically ordered for each patient, and reassembled into one-year episodes of care for both pre- and post intervention periods to acquire the cost-savings impact of the intervention at the patient-level. Thus, a patient's individual cost-savings as well as a comparison against the routine care group's mean will be obtained.

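### The promised comparison of clinical outcomes has no defined events and no suitable analysis, and the dropout rule can remove the patients who have those events

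*Combined protocol and SAP*

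**What the plan says.** Statement of the Problem commits to a comparison: "We will also compare health care costs, symptoms, quality of life, and clinical outcomes between the two groups". Purpose of the Current Proposal repeats this as a secondary analysis. Key Question #2 asks whether outcomes, repeat hospitalizations among them, are equivalent or superior to those of PCI.

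The analysis paragraph for Key Question #2 in the Statistical Analysis Plan starts with peak VO2 and other exercise-test responses and ends with "exercise time, and heart rate recovery), quality of life measures, and lipid panels". Change is compared between groups by repeated measures ANOVA on baseline and 1-year values. Repeat hospitalizations do not reappear, and no other clinical event is named.

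Event-like information appears in three other places:
- Cost Effectiveness Analysis tracks utilisation from the VA record: "inpatient and outpatient visits, events, hospitalizations, procedures and prescriptions". Hospitalizations and ER visits are compared and then valued in money.
- The CT part of the PET/CTA Study Protocol grades a lesion needing PCI or bypass as +3 and adds it to the patient's other lesion grades.
- Study Procedures has ST depression measured at exercise tests and sets arrhythmia definitions: "Ventricular tachycardia will be defined as three or more consecutive premature ventricular contractions". Table 1 schedules these tests at baseline, 6 months and 1 year.

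On missing patients, Sample Size Estimates states: "Dropouts will not be included in the statistical analyses".

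**The concern.** The trial aims to support exercise as an alternative to PCI in patients referred for PCI. A reader of the results will first ask how many patients in each arm died, had an infarction, or needed an unplanned procedure. The protocol promises an answer under clinical outcomes, but the analysis section does not deliver one.

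The dropout rule makes this more than a missing detail. The patients it removes are not a random subset, because death or withdrawal after a cardiac event is itself a reason to have no 1-year scan or exercise test. Such a patient has no value for Key Question #1 or #2, and none for the cost-effectiveness measure, whose effect is the 1-year change in perfusion reserve. Read literally, the rule also takes the patient out of the cost comparison. The trial could then report favourable perfusion, fitness and cost results without counting those events in either arm.

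**Working it through.** **1. The plan's own figures.** From Sample Size Estimates: SD 0.20 at both visits, correlation 0.65, target difference 0.15 × 0.9 = 0.135.
- SD of change = √(0.20² + 0.20² − 2 × 0.65 × 0.20 × 0.20) = 0.1673. The plan agrees: "the standard deviation of the change in myocardial blood flow is 0.167".
- Effect size 0.135 / 0.167 = 0.81. The normal-approximation formula gives 25 per arm, again as stated: "Using a 2-sided significance level of 0.05 and 80% power, 25 subjects in each group will be needed to complete the protocol".
- Allowing for 20% dropout: 25 / 0.80 = 31.25, rounded up to 32 per arm and 64 in total.

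The sample size reproduces, but it rests on the PET endpoint alone.

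**2. Who can be lost.** 32 − 25 = 7 per arm, or 0.20 × 32 = 6.4 expected dropouts per arm.

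**3. What the loss can hide.** Suppose, for illustration, that 3 exercise-arm patients have an event and all 3 are among the dropouts.
- Completers only: 0 of 25. Exact two-sided 95% upper limit 1 − 0.025^(1/25) = 13.7%.
- All randomised: 3 of 32 = 9.4%. Exact 95% CI 2.0% to 25.0%.

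With no events at all, 0 of 32 gives an upper limit of 1 − 0.025^(1/32) = 10.9%.

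**4. How many events to expect.** The only rate given for this population is in Study Population: annual mortality below 1%.
- Deaths: at most 32 × 0.01 = 0.32 per arm and 0.64 in all. The chance of at least one death in the trial is at most 1 − 0.99^64 = 47%.
- Composite of cardiac events: no rate is given. Assumed rates of 5%, 10% and 20% give 1.6, 3.2 and 6.4 expected events per arm of 32.

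**5. Could 64 patients support a test?** All rates below are assumptions.

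| Assumed rates | Power at 32 per arm (normal approx.) | Power (Fisher) | Needed per arm for 80% |
|---|---|---|---|
| 5% vs 15% | 26% | 11% | 141 |
| 10% vs 20% | 20% | 11% | 199 |
| 10% vs 30% | 52% | 41% | 62 |

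Fisher's exact test on 5 of 32 versus 0 of 32 gives p = 0.053, and 6 versus 0 gives p = 0.024. Only a large excess would reach significance, so counts with intervals are what this size supports.

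**6. Does the lesion score stand in for revascularisation?** One revascularised lesion (+3) and three regressing lesions (−1 each) sum to 3 − 3 = 0, the same as no change. A patient who dies has no 1-year CT to score.

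**The case against.** Several stronger readings are tempting, and the documents do not support them.

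- *That cardiac harms are fully recorded and simply left unanalysed.* Death and infarction are never named as collected. They could enter only under the generic terms for events and hospitalizations in the cost section. The fix therefore needs some definition work as well as a new table.
- *That nothing event-like is compared between arms.* Hospitalizations and ER visits are compared as cost inputs, and revascularisation feeds a lesion score that is a secondary outcome. Neither isolates a cardiac event, but the gap is in the analysis of events as such.
- *That exercise-induced ischaemia and arrhythmia are excluded.* The exercise-test list is open-ended, so these findings are unspecified. ST depression in millimetres could go into the ANOVA; yes/no arrhythmia findings could not.
- *That deferring PCI is a known harm.* Rationale for the Current Proposal reports that in a sub-study "a greater improvement in percent of ischemic myocardium, a predictor of mortality, was observed in patients who underwent PCI". It adds that this sub-study sample was not randomised and that the result conflicted with the main trial, which found no PCI effect on death or infarction. The same section says deferral is safe. The risk is plausible, not established.
- *That a death would count as a saving.* The dropout rule may remove it from the cost analysis. If it is kept, shorter follow-up could lower cost and a terminal admission could raise it, so the direction is unknown.

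It is also fair to say that entry is restricted to patients with a good prognosis, so few deaths are expected. Some front matter and the appendices are not in the public text. The protocol describes the appendices as a flow chart, questionnaire and log material and a timeline, but a safety section elsewhere cannot be ruled out.

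None of this supplies an event definition, an analysis population or a method.

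**Conclusion.** The concern holds in this form: a comparison of clinical outcomes is promised, but no event is defined or analysed, and the stated dropout rule can remove exactly the patients who have events. That rule can bias what is reported, and it should be changed. Up to 7 of 32 patients per arm are affected under the plan's own allowance.

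The conclusion assumes that a patient who dies or withdraws after an event counts as a dropout. The plan does not define the term, but sizes the trial on patients who complete the protocol. The illustration of 3 hidden events and all composite rates are assumptions. The point does not show that exercise is harmful, nor does it call for a larger trial. It concerns complete reporting with honest intervals.

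**What to change.** In the Statistical Analysis Plan and Sample Size Estimates:

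1. Exempt clinical events from the dropout exclusion.
2. Define death, myocardial infarction, unplanned revascularisation (not counting the assigned index PCI) and cardiac hospitalization. Ascertain them the same way in both arms, from the medical record already being extracted.
3. Report them descriptively by assigned arm for all 64 randomised patients, to 1 year or last contact: number with an event, follow-up time (or a Kaplan-Meier estimate) and exact 95% CIs. Make no significance claim.
4. Tabulate exercise-induced ST depression, ventricular tachycardia and frequent premature ventricular contractions by arm at 6 months and 1 year among those tested, with the number tested and baseline status. Avoid logistic models, which are likely to be inestimable for rare arrhythmias with about 25 per arm.
5. Show deaths next to the cost result.
6. Note that Subject Burden gives about 38 visits in the exercise group and about 8 in the PCI group, so detection may be unequal.

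The cost is event-definition work, some follow-up of dropouts through the record, and two descriptive tables. Sample size, treatment and scheduled visits do not change. The price is wide intervals in print: even 0 of 32 leaves up to 10.9% possible, so any statement about exercise as an alternative will have to be more cautious.
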